Specific Aim 1: To assess the difference in the intraoperative and postoperative opioid consumption in patients receiving a supra-serratus versus a sub-serratus approach to the SAPB.

Specific Aim 2: To compare post-operative Visual Analog Scale (VAS) scores relative to baseline preoperative VAS scores, patient postoperative pain satisfaction scores, presence of nausea or vomiting, hospital length of stay, sleep duration in first 24 hours post-operation and block performance times in the two serratus anterior plane techniques.

Primary Endpoint:

- Opioid consumption during the 24 hours following placement of the serratus anterior plane block

Secondary Endpoints:

1. Change in immediate post-operative pain scores from their pre-operative baseline, stratified to type of surgery
2. Pain scores during the first 24 hours after placement of the block, stratified to type of surgery
3. Patient satisfaction with regards to their perioperative pain control during the first 24 hours after placement of the block, stratified to type of surgery
4. Presence of nausea or vomiting
5. Length of stay
6. Duration of sleep during the first post-operative night
7. Block performance time

2. Background:

The serratus anterior plane block is used for postoperative pain controls in surgeries involving the anterolateral chest wall, including breast surgeries and thoracic surgeries located on the anterior or lateral portions of the chest wall^{2,5}. These include breast surgeries, anterolateral thoracotomies, pain control in multiple rib fractures, and even as an adjunct to control upper thoracic pain in shoulder surgeries^{4,6-8}. The initial description of the block by Blanco et al. included two possible techniques that were both effective at producing sensory blockade to the anterolateral chest wall. While both were effective in volunteer patients, it was not determined if one approach was more effective than the other at post-operative pain control. The two methods, the supra-serratus approach and the sub-serratus approach to the serratus anterior plane block, are described below.

Supra-Serratus Anterior Plane Block, adapted from Blanco et al.:

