The patient will undergo a standard anesthesia pre-operative history and physical exam, and the risks, benefits and alternatives of general and regional anesthesia will be discussed with the patient. An informed written consent for clinical care will be obtained from the patient. If SAPB is an appropriate component of the patient's anesthetic, and the patient has consented to receive a SAPB, the patient will then be introduced to the study. After discussing the study procedure, its risks, benefits, and alternatives, and answering all questions with the study candidate, an informed written consent for study participation will be obtained.

Once enrolled, a patient will be randomized to one of two groups: the supra-serratus anterior plane block (depositing local anesthetic superficial to the serratus anterior muscle) or the sub-serratus anterior plane block (depositing local anesthetic deep to the serratus anterior muscle). Randomization will be performed using a computer generated randomization program. The results of the randomization will be revealed to the physician performing the block just prior to its performance. The site of the block will be marked and a safety timeout will be performed with the block nurse, regional anesthesiologist, and patient present and participating.

Once the above is completed, patients will receive a preoperative ultrasound-guided single-injection serratus anterior plane block using either the supra-serratus or sub-serratus techniques according to their randomization. The block nurse, who is blinded to the approach, will record the time when the timeout is performed, the “needle insertion” time when the block needle enters the skin, and the “block complete” time when the needle exits the skin. If the block is bilateral, the block nurse will record the time when the timeout is performed, then will record two sets of “needle in” times and “needle out” times, one for each side. In the case of a bilateral block, the same method of serratus anterior plane block will be utilized for both sides.

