- Potential subjects will be identified by reviewing the operating room daily schedule via the electronic medical record (EPIC) or in the anesthesia preoperative clinic. The EMR will be used to prescreen potential study candidates.

- Recruitment and consent will occur in the Anesthesia preoperative clinics or the Day Surgery Unit at William P. Clements Jr. University Hospital.
- Randomization will be performed using a computer generated randomization list.
- **Serratus Anterior Plane Blockade:**
 - The serratus anterior plane block will be performed using a linear HFL38xp ultrasound probe (x-Porte; SonoSite; Bothell, Washington). The patient will be positioned in the lateral decubitus position with the side to be blocked facing up. The patient will be positioned with their arm resting comfortably above their head to expose their axilla and lateral chest wall. Using the ultrasound probe and anatomical landmarks, the 4th and 5th ribs will be identified at the mid to posterior axillary line. Superficial to the ribs at this location, the serratus anterior muscle will be identified. The latissimus dorsi muscle will be identified in the same plane superficial to the serratus anterior. The skin at the needle insertion site will be sterilized with chlorhexidine gluconate 2% and 70% isopropyl alcohol prep. A skin wheal of lidocaine 1% (2-5mL) will be delivered. A short-beveled, non-stimulated block needle (SonoTap, 21 gauge), will be inserted through the skin wheal under continuous ultrasound guidance towards the target plane location (either above or below the serratus anterior muscle, determined by randomization). Local anesthetic will be injected into the tissue plane described above. 30 mL Ropivacaine 0.35% will be used on each side for patients weighing over 60 kg, and 20 mL Ropivacaine 0.35% will be used on each side for patients weighing less than 60 kg. The weight-adjusted difference in volume is employed to maintain a safe total dose of local anesthetic, while controlling for drug concentration. Adequate spread of the local anesthetic will be confirmed with direct ultrasound visualization.

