The patient's vital signs will be monitored before, during and after placement of the SAPB. Any adverse reaction would be quickly detected by anesthesiology staff or perioperative nurses. Adverse reactions will be appropriately treated immediately and placement of the block will be discontinued if not yet finished. Serious adverse events will be reported to the IRB.

The primary investigator will supervise all data collected.

12. Procedures to Maintain Confidentiality:

A numerical code will be used to refer to each patient case and all data gathered for that case will be associated with the numerical code. Direct patient identifiers will not be used during data analysis. A key, linking the numerical code with specific patients will be employed in order to review patient charts for additional study information (such as pain scores, opioid usage, antiemetic usage, and length of stay). Only de-identified study data will be recorded in a database on an encrypted, password protected, secure server. Once the study data has been gathered and analyzed, the key to the numerical coding system will be destroyed.

All protected health information will be kept in a secure location with access limited to study investigators only.

13. Potential Benefits:

The study may help the medical community by determining if there are notable differences in the analgesic efficacy between two potential locations of the serratus anterior plane block. This has the potential to improve patient pain scores and satisfaction while reducing perioperative opioid usage and potentially shortening length of hospital stay by avoiding adverse side effects of opioid consumption (such as ileus, nausea, vomiting, and confusion). Improvement in pain control may also lead to improved sleep duration on the first post-operative night, which may further improve patient satisfaction and decrease potential for delirium or confusion.

14. Biostatistics:

Assuming a standard deviation of 32 units, the study will need a total sample size of 58 (29/group) to detect a 20% difference in mean opioid consumption during the 24 hours (an effect size of 0.75) following placement of the serratus anterior plane block between the two groups. Accepting loss of follow-up data on 10% patients, the study will randomize a total of 66 patients on a 1:1 ratio between supra-serratus and sub-serratus block group.

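### No stratification factor is specified for allocating 66 patients, although surgery type is singled out for three secondary endpoints and the planned tests do not adjust for it

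*Combined protocol and SAP*

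**What the plan says.** Allocation is described in three places. Section 3 says "Randomization will be performed using a computer generated randomization program". Section 4 says "Randomization will be performed using a computer generated randomization list". Section 14 says "the study will randomize a total of 66 patients on a 1:1 ratio between supra-serratus and sub-serratus block group". None names a stratum, a block or a minimization rule.

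The population is mixed. Section 6 admits mastectomy and mastectomy with tissue expander. Section 3 also allows one- and two-sided blocks: "In the case of a bilateral block, the same method of serratus anterior plane block will be utilized for both sides".

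Section 1 singles out surgery type for secondary endpoints 1-3. Endpoint 2, for example, reads "Pain scores during the first 24 hours after placement of the block, stratified to type of surgery". Section 14 then compares the groups with a t-test or Wilcoxon-Mann-Whitney test, and with Fisher's test for nausea and vomiting. It mentions no covariate or stratum, even for the endpoints that Section 1 calls stratified. Type of surgery is among the data that Section 3 says will be recorded.

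**The concern.** By asking for three endpoints by surgery type, the plan signals that it expects the operation to matter for pain and satisfaction. If it also matters for opioid use, a chance surplus of one operation in one arm moves the observed 24-hour difference, and the planned tests cannot separate that movement from the effect of the block.

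The factor could be balanced in advance. Candidates are found from the operating room schedule and chart review, and the assignment is revealed just before the block (Section 3), so the planned operation should be known at allocation. An imbalance can be adjusted for later, but the allocation itself cannot be redone.

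**Working it through.** **1. The plan's own figure.** Section 14 gives "Assuming a standard deviation of 32 units" and "an effect size of 0.75", so the design difference is 0.75 × 32 = 24 units. Power and sidedness are not stated. With two-sided 0.05 and the noncentral t distribution, power is 78.7% at 28 per arm and 80.1% at 29 per arm. The stated 58 is therefore reproduced if 80% power was intended. Allowing for 10% loss, 58 / 0.9 = 64.4, rounded up to 65, and to 66 for equal arms.

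**2. Chance of imbalance.** Let K of the 66 patients have one of the two operations, and let x of them fall in one arm of 33. Then x is hypergeometric, and the difference between arms in the share with that operation is (2x − K)/33. Its standard deviation is (2/33) × √[33 × (K/66) × (1 − K/66) × (33/65)]. The documents give no shares, so 20-50% is assumed.

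| Assumed share | K | SD of difference (points) | P(15 points or more) | P(20 points or more) |
|---|---|---|---|---|
| 20% | 13 | 9.9 | 21.5% | 6.1% |
| 30% | 20 | 11.4 | 18.0% | 5.9% |
| 40% | 26 | 12.1 | 20.7% | 7.7% |
| 50% | 33 | 12.4 | 32.5% | 13.9% |

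The columns do not rise steadily because x is a whole number. At a 50% share, 15 points means a split of 19 v 14 or worse. Among 29 v 29 evaluable patients, the 20-point chance is about 8-11%. If the list were a pure coin toss it would also be about 8-11% (shares of 30% and 50%), and arm sizes of 38:28 or worse would occur 27% of the time.

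**3. What an imbalance does.** The observed difference shifts by the imbalance times the gap in mean opioid use between the operations. The documents give no gap. For 20 points, a gap of 8 units shifts the difference by 0.20 × 8 = 1.6 units, and a gap of 32 shifts it by 0.20 × 32 = 6.4 units. That is 7-27% of the 24-unit target. The standard error of the difference is 32 × √(2/29) = 8.4 units.

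**4. What the remedy buys.** Let p be the share and g the gap. Adjusting for surgery type reduces the residual SD to √[32² − p(1 − p)g²]. Without stratified allocation, chance correlation between arm and operation raises the adjusted variance by about 1/(58 − 1) = 1.8% on average. At p = 50%, 29 per arm and a true difference of 24 (noncentral t, 55 degrees of freedom):

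| Gap g | Residual SD | Power, adjusted only | Power, adjusted and stratified |
|---|---|---|---|
| 8 | 31.7 | 80.1% | 80.7% |
| 16 | 31.0 | 81.9% | 82.6% |
| 24 | 29.7 | 85.1% | 85.7% |

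The planned unadjusted test has 80.1%. For one factor, stratified allocation thus adds about 0.6-0.7 points. Simulations with two prognostic factors, both stratified and adjusted, gave 82.5% against 84.7% (factor effects of 16) and 89.7% against 90.3% (effects of 24). Hence the range of about 0.5-2 points.

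**5. Balance after the remedy.** With two lists, permuted blocks of 4 and a 50:50 mix, the largest difference in 20,000 simulated trials was about 4 points. With four lists (surgery type by laterality) it was about 10-11 points.

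**The case against.** The strongest reply is that this is a design preference. The SD of 32, if it describes the whole population, already contains the variation between operations, so chance imbalance is already in the t-test's standard error. Simulation of the planned unadjusted test without stratification gave 80.2-80.5% power, averaged over imbalances, with factor effects of 8, 16 or 24. Prespecified adjustment alone would recover most of what a strongly prognostic factor costs. All of this stands, and it limits the point to precision and to the credibility of a single result.

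A reader might infer more than the documents support:

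- **That the list is known to be unstratified.** The plan is silent. The supportable statement is that no factor is specified.
- **That Section 1 contradicts Section 4.** The wording in Section 1 concerns how endpoints 1-3 are reported. It does not require stratified allocation.
- **That laterality must also be a stratifier.** No section treats it as prognostic for opioid use. It does lengthen block time by construction, because Section 3 times a bilateral block from the first needle entry to the second needle exit. A covariate handles that.
- **That surgery-type comparisons would rest on very lopsided splits.** With a 30% share the smaller stratum has about 20 patients, and a split of 15:5 or worse has a 1.5% chance.
- **That imbalance would cut power sharply.** This needs a gap between operations as large as the whole design difference, which no document gives, and it looks only at imbalances in the unfavourable direction.

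Predictability is a genuine cost. The performing physician learns each assignment, and anesthesiology staff recruit. With four lists and blocks of 2 and 4, someone who knew every earlier allocation in a stratum could guess the next one correctly 71% of the time, against 50% under simple randomization.

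**Conclusion.** The point holds in limited form. As written, neither allocation nor analysis controls for surgery type, which the plan itself singles out and already records. A clear imbalance is a minority outcome: about 18-32% for 15 points or more and 6-14% for 20 points or more on this one factor. It leaves the type I error intact, but it costs precision and can distort the one result the trial will produce. The remedy is worth making because it is cheap, not because the present design is invalid.

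These figures assume a 20-50% share for one operation, exact 33/33 allocation, a two-sided test and 80% intended power. The power gains also depend on the assumed gap in opioid use. If that gap is small, adjustment gains almost nothing and only the small benefit of balance remains.

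**What to change.** 1. **Sections 3 and 4.** State that the computer-generated allocation uses two permuted-block lists, one for planned mastectomy and one for planned mastectomy with tissue expander. Block sizes should vary at random and be kept from recruiting and block-performing staff. Use the planned operation, not the one performed, so that the stratum is fixed before allocation.
2. **Section 14.** Include surgery type in the between-group comparisons of 24-hour opioid use and of secondary endpoints 1-3, by a linear model or, if normality fails, a stratified rank test such as van Elteren's. This should accompany the stratified lists, because an unadjusted test after stratified allocation is conservative: in simulations with two stratified factors its type I error was 2.7-3.8%.
3. **Laterality.** Handle it as an analysis covariate, above all for block performance time. Four strata at 66 patients would be small and would balance less tightly.

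The cost is a second list, a sentence in each of Sections 3 and 4, and a rewritten analysis paragraph in Section 14. No extra patients, visits or data are needed. The named downside is slightly greater predictability of allocation, which varied and concealed block sizes reduce but do not remove.
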